4. STUDY FLOW CHART

TIME	Informed Consent	Medical History	Phys. Exam, ECG, Vital Signs, Pulse Ox	Lab Tests, Drug Screen	Pregnancy Test Females	Dosing	Pin Prick= P Heat Sensation Threshold= H (PPT & QST)	Blood Draw	AE Assessment
Screening	√	√	√	√	√		P (both cheeks), H (both cheeks)	√	√
Test Session 1		√	√	√*	√		P (both cheeks), H (treated cheek)	√	√
Test Session 2		√	√	√*	√		P (both cheeks), H (treated cheek)	√	√
-5 min									√
0 hr						√			√
1, 2, 3, 4 min							P (both cheeks)		√
5, 15, 25, 35, 45, 55 min							P (both cheeks), H (treated cheek)		√
10, 20, 30, 40, 50 min			√***				P (both cheeks), H (treated cheek)		√
60min			√				P (both cheeks), H (treated cheek)	√	√
Discharge									√
3 or 15-Day Call**									√

* Urine Drug Screen Only

**After Session 1, 3-Day Follow-up Call ± 1 day; After Session 2, 15-Day Follow-up Call ± 2 days

*** Pulse Oximetry Only, if <91%, the subject will be discontinued from the study

P=pinprick evaluation; H=heat tolerance evaluation

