ESTIMATED DURATION OF SUBJECT PARTICIPATION IN THE STUDY:

The subjects will be tested on two separate occasions. Each session will take approximately two hours total time; however, the actual efficacy testing will take 60 minutes. There will be 4-14 days spacing between visits. A phone follow-up will occur 3 days (\pm 1 day) and 15 days (\pm 2 days) after the subject completes Sessions 1 and 2, respectively. If there are any adverse side effects, at the discretion of the PI, the subject may be asked to return to the study site for evaluation.

DURATION OF STUDY:

The study will be completed when the last subject completes the last follow up phone call. The expectation is that the study will be completed within 4-6 months of the first subject entry.

NUMBER OF SUBJECTS:

Up to 150 male and female subjects will be screened in order to enroll up to 76 ASA Category I or II subjects. The total number of exposures to study medication will be 152 (76 subjects x 2 exposures). Each of the CTY-5339-A treatment regimens will have 38 exposures and the CTY-5339-CB will have 76 exposures.

SAMPLE SIZE DETERMINATION:

The sample size was selected based on evaluating a reasonable number of subjects to determine whether CTY-5339-A has a longer duration of action than CTY-5339-CB, which contains 14.0% benzocaine only.

DOSAGE:

(specific gravity is slightly less than 1; therefore 200 μ L is an approximate volume.)

CTY-5339-A 1-metered spay = 200 mg total (\approx 200 μ L)
Benzocaine 28 mg + Tetracaine HCl 4 mg

CTY-5339-A 2-metered spays = 400 mg total (\approx 400 μ L)
Benzocaine 56 mg + Tetracaine HCl 8 mg

CTY-5339-CB = 200 mg (\approx 200 μ L)
Benzocaine 28 mg

INCLUSION CRITERIA:

- a. Male and female subjects between 18-75 years of age with a Body Mass Index (BMI) \leq 32;
- b. Subjects are ASA Category I or II and are in good physical health as judged by physical and laboratory examinations;
- c. Subjects with normal appearance of the oral mucosal tissues;
- d. At screening and at Baseline during Session 1, subjects with PPT scores on both cheeks of at least "3" (on a 10 point NRS) on the last 2 of 3 readings, 1 of which must be a score of at least "4";
- e. Subjects with mean QST Heat sensation temperature assessments

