QST: The heat stimuli are delivered in 3 repetitions, with inter-stimulus intervals of 30s. The basal thermode temperature is set at a comfortable 35°C. The rate at which the thermode heats up is set at 0.5°C/s, while the rate at which it cools down is set at 8°C/s. The maximum thermode temperature is set at 51°C. The first stimulus is disregarded and the remaining two stimuli are averaged for data analysis. In situations where a maximal analgesia/anesthesia effect is demonstrated in the initial two repetitions, the QST test will not be repeated for the third repetition and the data will be recorded as maximal effect (51°C) based on the first two repetitions.

Heat sensation threshold will be defined as the temperature at which the subjects first start to feel tingling, warmth, heat, or pain. All tests will be done near the center of the circumscribed area, but in a different place at each evaluation time point. For QST, the first time point after Baseline will begin at 5 minutes after drug administration. Subjects will have a hand held mouse that turns off the heat probe when they first start to feel tingling, warmth, heat, or pain. At the maximum heat level of 51° C, the heat probe turns off automatically. With a brief exposure at 51° C, there is no damage to the mucosal tissue.²⁵

Randomization: A randomization code will determine in which circumscribed area each treatment is administered (left or right cheek). Immediately prior to beginning each 60 minute test session, both the contra-lateral cheek and the cheek to be dosed will be evaluated with the PPT. For QST, the screening assessments will be performed on both cheeks, while during each treatment Session, at Baseline and all post-dosing time points, assessments will be performed on the treated cheek only.

Subjects retain the right to withdraw from the study at any time.

The PPT and QST tests will be done near the center of each evaluation area but in a different place at each evaluation time point. For PPT, the non-treated control cheek will always be tested before the treated area. The testing will be done in the following order where applicable: PPT and then QST.

A safety phone follow-up call will occur 3 days (± 1 day) after the Session 1 and 15 days (± 2 days) following Session 2.

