11.4 Safety Assessments

Adverse events will be recorded when they are reported or observed. The AE collection period will begin at the time the subject is initially screened and continue for 15 days after the subject's last administration of study medication. Only the PI will determine the relationship to study medication for each AE prior to breaking the blind. The information will be recorded on the appropriate study center CRF and outpatient diary. In addition, vital signs (DBP, SBP, HR) will be assessed at the beginning and end of each 60 minute test session.

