12. SAFETY

12.1 Subject Examinations

To ensure the safety and well-being of each subject entered into the study, the subject must first be examined by the PI or Sub-Investigator and medically cleared to participate as required by the protocol. Each subject will be observed for adverse events (AEs) and will be required to report any adverse events that develop during the course of the study and for 15 days post-drug treatment. If at any time during the study, the subject has a serious adverse event (SAE) or abnormality, the subject must be withdrawn from the study and appropriate care should be initiated.

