12.4.4 Adverse Event Recording and Reporting

All AEs, whether serious or not, will be recorded on source documents and CRFs. The recording period for AEs and SAEs starts at the time the subject is screened. The recording period for both AEs and SAEs lasts through 15 days after the subject's last administration of study medication, regardless of the relationship to the study medication. The PI must follow up as medically necessary on all AEs, SAEs, and other reportable events until the event has subsided or values have returned to baseline, or in the case of permanent impairment, until the condition stabilizes.

For SAEs, the PI will provide all documentation pertaining to the event (*e.g.* additional laboratory tests, consultation reports, discharge summaries, postmortem reports, etc.) to the Cetylite Medical Monitor in a timely manner. Reports relative to the subject's course must be submitted to Cetylite until the event has subsided or, in the case of permanent impairment, until the condition stabilizes.

Information about all adverse events, serious and non-serious, including the event's severity, start and stop times/dates, chronicity, relatedness to study medication, and any actions taken, must be recorded on the appropriate CRFs. The information recorded will be based on the signs and symptoms detected during the physical examination and clinical evaluation of the subject as well as information recorded in the subject's diary, when applicable.

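### The only prompted 15-day safety call is tied to Session 2, so a subject dosed only at Session 1 who does not return gets no closing adverse event question

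*Combined protocol and SAP*

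**What the plan says.** The recording period is anchored to the last dose. Section 11.4 states: "The AE collection period will begin at the time the subject is initially screened and continue for 15 days after" the last administration of study medication. Section 12.4.4 agrees: "The recording period for both AEs and SAEs lasts through 15 days after" that same point. Section 12.1 puts a matching duty on subjects, who "will be required to report any adverse events that develop during the course of the study and for 15 days post-drug treatment". The safety evaluation part of the synopsis also accepts voluntary reports, within 3 days of the first session and within 15 days of the end of the subject's participation.

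The prompted contacts are anchored to sessions. The flow chart footnote schedules a 3-day call (± 1 day) after Session 1 and "After Session 2, 15-Day Follow-up Call ± 2 days". The synopsis places the two calls "after the subject completes Sessions 1 and 2, respectively", and section 9 has the second call "15 days (± 2 days) following Session 2". In the flow chart, the only adverse event row after discharge is the one for these two calls.

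The protocol foresees subjects who receive one dose only. Section 9 allows withdrawal at any time, and section 11.7 lists grounds for individual discontinuation. Sections 11.5 and 12.4.6 stop the whole study on a finding in a single subject: oximetry below 91%, methemoglobin above 5%, or a serious adverse event not shown to be unrelated. None of these sections adds a closing contact for subjects who have had one dose.

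**The concern.** The window follows the last dose and the closing call follows Session 2. For a subject dosed at both sessions these coincide. For a subject dosed once who does not come back they do not, and nothing in the text moves the 15-day call to the Session 1 dose.

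At stake is prompted ascertainment of new, delayed events that the subject does not volunteer. Infection at the application site, which the synopsis says will be assessed, is an example of something that could appear after day 4. The gap would be most awkward after a study-wide stop. The subject who triggered the stop is followed until the event settles, but others who had received one dose would have no scheduled final question, at the moment when complete safety data are most wanted.

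**Working it through.** The plan gives no figure to reproduce; the check is day counting from the last dose (day 0).

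**Inputs**
- End of the recording window: day 15 after the last dose (sections 11.4, 12.4.4).
- Call after Session 1: 3 ± 1, so day 2 to 4 (flow chart, section 9, synopsis).
- Call after Session 2: 15 ± 2, so day 13 to 17 (same places).
- Gap between sessions: 4 to 14 days (synopsis, section 9).

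**Days of the window left after the last scheduled prompt** = 15 − day of last call, with a minimum of 0
- Dosed only at Session 1, no return: 15 − 4 = 11 to 15 − 2 = 13 days.
- Dosed at both sessions: 15 − 13 = 2 days at most, and 0 if the call is on day 15 or later.

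**Longest stretch without a prompt after the last dose**
- Dosed only at Session 1: 11 to 13 days, from the call on day 2 to 4 to the end of the window.
- Dosed at both sessions: 13 to 17 days, from the Session 2 dose to the call.

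The silent stretch is thus no longer for the one-dose subject. The two differ in what ends it: one closing question for the completer, none for the one-dose subject.

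**Attending Session 2 without being dosed.** A subject who fails the Session 2 baseline thresholds (section 11.7, item e) is seen on day 4 to 14, and the flow chart ticks an adverse event assessment there. Whether the 15-day call then applies is unclear: the synopsis speaks of completing the session, while the flow chart and section 9 refer only to the time after it. The full gap therefore applies to non-returners.

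**After the fix.** With the call 15 ± 2 days after the last dose received, the one-dose subject is contacted on day 13 to 17, leaving 0 to 2 days of the window after the prompt, as for a completer. The timing is workable: the longest permitted gap ends on day 14, so by then the site knows that no second dose will follow, and days 15 to 17 remain for the call.

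**The case against.** The strongest reply is that the adverse event window has no hole. Sections 11.4, 12.1 and 12.4.4 cover every dosed subject for 15 days, whichever session they reached. The synopsis adds voluntary reports up to 15 days after the end of participation, which covers an early leaver. Section 11.4 also names a diary ("The information will be recorded on the appropriate study center CRF and outpatient diary"), though section 12.4.4 qualifies it as "diary, when applicable". Known events are followed until they subside or stabilize, and section 12.3 keeps an investigator or designee available throughout the study. All of this stands. A reader might infer that events after day 4 go uncollected in one-dose subjects; the documents do not support that. Only the prompt is missing. Even so, the sponsor chose to schedule a closing call for completers on top of passive reporting, and no reason is given for omitting it in subjects who stop early.

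It can also be said that few subjects are affected and that some, having refused to continue, would be hard to reach. That is fair, and the fix exempts anyone who refuses further contact.

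A reader might take the statement in section 11.7 that discontinued subjects record no further assessments as forbidding a safety call. That is not a sound reading: the sentence deals with efficacy data, and the next one expects follow-up safety data.

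**Conclusion.** The mismatch is real and small: one missing closing prompt for each subject who is dosed only at Session 1 and does not return. It rests on the call schedule as written in three places and on the absence of any early-termination contact. Efficacy is unaffected, and the safety measurements scheduled within each 60-minute session do not depend on the call.

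Two stronger readings should be avoided. The first is that only 2/15 = 13% to 4/15 = 27% of the window is covered, against 13/15 = 87% to 15/15 = 100% for completers. Those fractions count days up to the last call and make one missing question look like a large loss of observation; the silent stretches are in fact similar.

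The second is a firm count of affected subjects. The documents give neither the number who will discontinue nor the chance of a stop. If enrolment were even (an assumption) and a stop came in mid-enrolment, the number between sessions would be 76 × gap / (study length − gap − 15), in days. Pairing the extremes gives 76 × 4 / (182.6 − 4 − 15) = 1.9 for a 4-day gap and a 6-month study, and 76 × 14 / (121.75 − 14 − 15) = 11.5 for a 14-day gap and a 4-month study. This counts subjects without a call, not missed events, and the conclusion does not depend on it. The supportable statement is that the number is unknown and probably small.

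**What to change.** In the synopsis (duration of participation), the flow chart footnote and section 9, keep the 3-day (± 1 day) call after Session 1. Then state that the 15-day (± 2 days) call is made 15 days after the last dose actually received, for every dosed subject who has not refused further contact. Name explicitly those who discontinue after Session 1 and those left with one dose when the study is stopped. Anchoring to the last dose also settles the case of a subject who attends Session 2 but is not dosed.

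A phrase in section 11.7 saying that the bar on further assessments concerns efficacy assessments is optional.

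The cost is amendment wording and one telephone call per subject dosed only at Session 1. No visit, test or analysis changes, and the schedule for completers stays as it is.

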APPENDIX 1: DESCRIPTION OF TESTING METHODS

Appendix 1A: Pin Prick Test (PPT)

Oral Mucosa sensation directly over the circumscribed sites will be assessed with a 90-mm, 26-gauge pencil-point spinal needle (Polymedical; Temena S.A., Bondy, France or its equivalent) at Screening, Baseline and predetermined intervals after application of drug. To standardize the methodology, all tests are performed by holding the needle at its hub and orienting it perpendicular to the oral mucosa surface. Pressure is applied until the needle shaft bows slightly. At screening a numerical score on a 0 – 10 pain intensity scale (NRS) is recorded for each cheek. After study drug administration, subjects are instructed to rate the pinprick sensation perceived over the circumscribed treatment site compared to that perceived at the contra-lateral circumscribed, non-treated site and to report the sensation as none, less, or similar/more to the non-treated site. Reports of none or less indicate analgesia, while a report of similar/more indicates complete regression of analgesia. At each observation, 3 pin pricks are performed first on the non-treated side, and then on the treated side. For each cheek, the first pin prick will not be used for analysis. Of the remaining two pin pricks, the one with the most severe pain rating will be used for the data analysis.

Appendix 1B: QST Heat Stimulus

1. This procedure uses the QST Heat Stimulator, a commercially available thermo-sensory analyzer (Medoc, [name]) that delivers heat stimuli to the oral mucosa with a blunt thermode that is 6mm in diameter. A central unit generates and transmits the signal to the thermode. This signal is controlled by proprietary software stored on a laptop connected to the central unit. Also attached to the central unit is a hand-held control (a computer mouse) that allows a study subject to stop the heating of the thermode. As the temperature is increased, subjects are asked to report when they first start to feel a tingling, warmth, heat, or pain sensation. The subjects are instructed to turn off the heat probe by depressing the mouse when they first start to feel tingling, warmth, heat or pain. The heat is applied in graded increments until the subjects depress the mouse or the temperature reaches the maximum of 51°C. At the maximum heat of 51⁰ C, the probe automatically turns off and tissue is not damaged. (Note: Hot beverages such as tea and coffee are frequently served at temperatures between 50⁰ C- 60⁰C.²⁵)

2. The heat stimuli are delivered, in three repetitions, with inter-stimulus intervals of 30s. The basal thermode temperature is set at a comfortable 35°C. The rate at which the thermode heats up is set at 0.5°C/s, while the rate at which it cools down is set at 8°C/s. The maximum thermode temperature is set at 51°C. For each assessment, the first stimulus is discarded and the remaining stimuli are

averaged, unless the first two readings are 51°C. In this case, the third assessment is not completed. At Baseline, and at each post-treatment time point, QST will be assessed on the treated cheek only.

APPENDIX 2: CRITERIA FOR A “RESPONDER”

PPT:

Based on “No Pain” or “Less Pain” response to the pain stimulus at each observation time when compared to the non-treated site, subjects will be classified as “Responders” or “Non Responders”. At each observation, 3 pin pricks will be performed at each site (first on the non-treated cheek and then on the treated cheek). The first pin prick will not be used for analysis. Of the remaining two pin pricks, the one with the most severe pain rating will be used for the data analysis. If the most severe pain rating at that time point is “No Pain” or “Less Pain”, then the subject at that time point is a “Responder”.

QST:

The actual temperature data will be recorded at each time point. Temperatures will be recorded for "first sensation of tingling, warmth, heat, or pain". Scores will be censored at 51°C, if no response is obtained. If the average heat sensation temperature at each time point is greater than the average heat sensation temperature at Baseline, then the subject at that time period will be considered a “Responder”.

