During each treatment session, at Baseline and at each post-dosing time point, 3 pin pricks will be performed first on the non-treated cheek and then on the treated cheek. At Baseline, pin pricks on both cheeks will be assessed using a 0 (no pain) to 10 (severe pain) NRS. Post-Baseline, pin pricks on the non-treated cheek will also be assessed using the 0 to 10 NRS, but on the treated cheek, the three repetitions will be compared to the non-treated cheek as "No pain", "Less Pain" or "Similar/More Pain". For each cheek, the first pin prick will not be used for analysis. Of the remaining 2 pin pricks, the one with the most severe pain rating will be used for analysis. During each treatment session, in order for a subject to be eligible to continue in the study, for each cheek, both of the last 2 Baseline assessment pin pricks must have a minimum score of "3" for the last 2 pin pricks, and one of those scores has to be "4" or higher. Post-Baseline, an assessment of "No Pain" or "Less Pain" at a drug application site will be recorded as presence of analgesia/anesthesia ("Responder").

Heat sensation threshold (QST-Heat): The heat stimuli are delivered in 3 repetitions, with inter-stimulus intervals of 30s. The basal thermode temperature is set at a comfortable 35°C. The rate at which the thermode heats up is set at 0.5°C/s, while the rate at which it cools down is set at 8°C/s. The maximum thermode temperature is set at 51°C. (Note: Hot beverages such as tea and coffee are frequently served at temperatures between 50°C - 60°C. Burns can occur at 65°C.²⁵). Heat sensation threshold will be defined as the temperature at which the subjects first feel tingling, warmth, heat, or pain.

At screening, QST-Heat assessments will be performed on each cheek. In order to be eligible for the study, for each cheek, subjects must have a mean Heat sensation threshold of 48.5°C or less, based on the last 2 of the 3 readings.

During each treatment session, for each assessment, the first stimulus will be disregarded and the remaining two stimuli will be averaged for data analysis (unless the first two readings are 51°C, in which case the third assessment will not be done). At Baseline and at each post treatment assessment, the heat sensation threshold will be performed on the treated cheek only. During each treatment session, in order for a subject to be eligible to continue in the study, subjects must have a

**STUDY
DESIGN: (cont)**

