mean Heat sensation threshold of 48.5°C or less, based on the last 2 of the 3 readings. Post-Baseline, the presence of analgesia/anesthesia will be defined when the heat sensation threshold at the treated site is higher than the Baseline (“Responder”).

All tests on the treated cheek will be done near the center of the circumscribed area, but in a slightly different place at each consecutive evaluation time point. All tests on the non-treated cheek will be performed at approximately the same part of the cheek as those on treated cheek.

Randomization: A randomization code will determine the sequence of treatments and to which circumscribed area the treatment is administered (left or right cheek). Sensory testing will be done in the following order: pin prick followed, where applicable, immediately by heat sensation tolerance.

Subjects retain the right to withdraw from the study at any time.

EFFICACY MEASUREMENTS

The primary comparison of interest is one spray of CTY-5339-A compared to one spray of CTY-5339-CB. Co-primary efficacy variables are duration of effect as determined by PPT and duration of effect as measured by QST Heat. Duration of effect is defined as the time (in minutes) from onset to treatment failure (for PPT, treatment failure occurs when an assessment of “Same/More” pain, and for QST, a treatment failure occurs when the average heat temperature is the same or less than the average heat temperature at Baseline up to the 60-minute time point (at two consecutive time points).

The secondary efficacy variables include:

- Duration of anesthesia (PPT and QST Heat) for the two sprays of CTY-5339-A compared to one spray of CTY-5339-CB plus CTY-5339-P
- Duration of anesthesia (PPT and QST Heat) for the two sprays of CTY-5339-A compared to one spray of CTY-5339-A
- Onset of anesthesia for PPT and QST Heat
- Percentage of responders for PPT and QST Heat for both onset and duration
- Percentage of responders for PPT and QST Heat at each time point

OTHER MEASUREMENTS

At Baseline and at the end of the 60-minute test session an ECG, vital signs, and a 7 mL blood draw will be taken. The blood will be analyzed for the occurrence of subclinical methemoglobinemia by the HUP – Pepper Lab via co-oximetry analysis. At screening and throughout each test session, subjects will also be monitored with pulse oximetry. Methemoglobinemia is being defined as >5% of a subject’s

hemoglobin in the methemoglobin state, or a pulse oximetry reading of less than 91%.

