13.5 Statistical Methods for Efficacy Evaluations

The primary efficacy analyses will be based on Modified Intent-to-Treat Population. The key comparisons will include:

1. CTY-5339-A, one spray versus CTY-5339-CB, one spray

The co-primary efficacy variables are duration of effect as measured by PPT and QST Heat. Duration of effect is defined as the time (in minutes) from onset to treatment failure (*i.e.*, for PPT, an assessment of “Same/More” pain, and for QST, the average heat temperature is greater than the average heat temperature at Baseline (non-treated cheek), up to the 60-minute time point (at two consecutive time points). For those discontinuing from the study for any other reason, the time to treatment failure will be censored at the last assessment time.

The secondary efficacy variables include:

- Duration of effect (PPT and QST) for CTY-5339A two sprays versus CTY-5339-CB, one spray plus CTY-5339-P one spray

- Duration of effect (PPT and QST) for CTY-5339A two sprays versus CTY-5339-A one spray
- Onset of anesthesia in minutes for PPT and QST Heat
- Percentage of responders at each time point for PPT and QST Heat for both onset and duration

Continuous variables will be analyzed via an ANOVA model with treatment effects at each of assessed time points. Pairwise comparisons for variables related to percentages will be analyzed via chi square tests. The 95% confidence intervals of the treatment differences will be presented using normal approximation with continuity correction, if appropriate. Pairwise comparisons for time-to-event related variables will be analyzed via a log rank model with treatment effects. Median time to event will be estimated and the 95% confidence intervals for the median will be presented, if appropriate.

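### Section 13.5 states the QST Heat failure rule in reverse, against a Baseline that is not taken; the zero-margin QST rule also merits one pre-specified sensitivity analysis

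*Combined protocol and SAP*

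**What the plan says.** **Responder.** The synopsis (Study Design) says "Post-Baseline, the presence of analgesia/anesthesia will be defined when the heat sensation threshold at the treated site is higher than the Baseline". Appendix 2 gives the same condition: "If the average heat sensation temperature at each time point is greater than the average heat sensation temperature at Baseline". Neither sets a minimum rise.

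**Failure, synopsis (Efficacy Measurements).** For QST, "a treatment failure occurs when the average heat temperature is the same or less than the average heat temperature at Baseline", and this must hold "up to the 60-minute time point (at two consecutive time points".

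**Failure, section 13.5.** The statistical section repeats the duration definition, but its QST failure condition is "the average heat temperature is greater than the average heat temperature at Baseline (non-treated cheek".

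**Where QST is measured.** The synopsis says "At Baseline and at each post treatment assessment, the heat sensation threshold will be performed on the treated cheek only", and Appendix 1B says "At Baseline, and at each post-treatment time point, QST will be assessed on the treated cheek only". Sections 9 and 11.2.3 agree. Only screening tests both cheeks.

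**Measurement and use.** Each value is the mean of the last two of three stimuli. QST runs every 5 minutes from 5 to 60 minutes, with onset required by 10 minutes. For duration, section 13.5 says "Pairwise comparisons for time-to-event related variables will be analyzed via a log rank model with treatment effects". Under section 13.6 either co-primary alone makes the study a success.

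**The concern.** Section 13.5 is the text from which the co-primary would be programmed. Its QST failure condition is the one that the synopsis and Appendix 2 use for response, so anesthesia would be scored as loss of anesthesia. The reference it names, a non-treated-cheek Baseline, does not exist within a session.

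A second, smaller question arises once the direction is put right. Any rise, however small, above a single two-reading Baseline counts as anesthesia. There is no concurrent QST control site, and ending the effect takes two non-rises in a row. Readings taken after the drug has worn off can therefore keep a session running by chance. Both primary treatments contain benzocaine, so both are exposed to this, and the difference between them could be blurred.

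**Working it through.** **Part A: the failure rule, side by side**

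| Place | Condition on the QST mean | Meaning | Reference |
|---|---|---|---|
| Synopsis, Appendix 2 | above Baseline | Responder | Baseline; session QST is on the treated cheek only |
| Synopsis, Efficacy Measurements | at or below Baseline, twice running | failure | Baseline, as above |
| Section 13.5 | above Baseline, twice running | failure | non-treated cheek, not measured in sessions |

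Now apply section 13.5 literally, substituting the treated-cheek Baseline because the named one is absent. Take a subject clearly anesthetized at 5, 10 and 15 minutes.

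- Onset is at 5 minutes.
- The first later pair of consecutive points above Baseline is 10 and 15 minutes.
- Dating failure at the first of the pair, duration = 10 − 5 = 5 minutes, whatever happens afterwards.

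Simulation with an assumed 3°C step effect and an assumed SD of 0.5°C gives a mean of 5.0 minutes for a true duration of 35 minutes and 5.0 for 20 minutes. With no effect at all, sessions with a chance onset average 18.8 minutes. The literal rule cannot separate the arms, and it scores an inert product as longer-lasting than an effective one.

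**Part B: the corrected rule, with zero margin**

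The documents give no QST noise, effect size or expected duration, and section 13.1 gives no power to reproduce. The only computable design figure is the alpha split, 0.10/2 = 0.05, which is correct. Everything below is illustrative. SD means the SD of a two-reading mean.

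1. After wear-off, Baseline and the next two means are exchangeable (equal error, no drift, no ties). Both later means fall at or below Baseline only if Baseline is the largest of three, so P = 1/3. With a 1 SD margin the simulated value is 0.633.
2. By the same argument a session with no drug effect shows onset by 10 minutes with probability 1 − 1/3 = 2/3.
3. A fixed 20-minute block of 4 SD is recorded as 36.7 minutes on average, with 35% of sessions unfailed at 60 minutes. With a 1 SD margin the figures are 26.6 minutes and 10%.
4. True durations of 35 and 20 minutes (3°C step, SD 0.5°C) are recorded as 46.0 and 36.7. The longer gains 46.0 − 35 = 11.0 and the shorter 36.7 − 20 = 16.7, so the difference falls from 15 to 9.3 minutes.
5. The direction is not universal. With a 0.5 SD step, true 35 reads 30 and true 50 reads 31. With a 1 SD step, true 50 reads 39.
6. Power of the unpaired log-rank test (two-sided 0.05, 38 pairs, lognormal durations, CV 50%, correlation 0.5, no onset counted as zero, failure dated at the first of two non-rises, censoring at 60 minutes):

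| Assumed effect | Zero margin | 1 SD margin |
|---|---|---|
| 30 vs 20 min, 4 SD block | 20% | 52% |
| 30 vs 20 min, 2 SD block | 15% | 27% |
| 30 vs 20 min, linear fade from 4 SD | 13% | 27% |
| 30 vs 20 min, linear fade from 2 SD | 9% | 13% |
| 50 vs 35 min, 1 SD block | 11% | 9% |

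In the first row the mean difference is 5.7 minutes with zero margin and 8.0 with the margin. For 50 vs 35 minutes at 2 SD, a paired t-test goes from 24% to 20% with the margin, so there the margin does not help.

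7. With equal true means and zero margin, type I error is 4.1–4.9%.

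**The case against.** On Part A, the section 13.5 wording is evidently a slip. The synopsis and Appendix 2 make the intent clear, and a careful programmer would probably query it. That is fair: nothing shows that the reversed rule would actually be run. It still stands uncorrected in the section that governs a co-primary analysis.

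On Part B, this is a proof-of-concept study. Section 13.1 accepts a clear trend, section 13.6 lets the pin prick endpoint carry success alone, and section 13.5 provides an ANOVA of continuous variables by time point. These points stand and limit the harm. They do not remove it: the trend is itself compressed, and the by-time-point analysis is not primary and is incomplete once QST is discontinued in a session.

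Three stronger readings are tempting, and the documents support none of them.

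- A reader might infer that noise always lengthens QST duration. Step 5 shows that weak long effects are shortened.
- A reader might infer a bias towards CTY-5339-A or a raised false-positive rate. The same rule applies to both arms, the shorter one gains more, and type I error stays at its nominal level.
- A reader might infer that the co-primary must be redefined with a margin. No margin has a basis in the documents, and its benefit depends on a noise SD and a wear-off shape that they do not give. It also costs onsets: for a fade from a 2 SD peak, sessions scored as no onset rise from about 10% to 30%.

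**Conclusion.** Section 13.5 is wrong as written on both the direction and the reference cheek of the QST failure rule. This conclusion needs no assumption about the data. Because it concerns a co-primary endpoint, it should be corrected before any programming.

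The zero-margin point is real but of lower severity. For short effects, or effects about 2 SD or more above the noise, recorded QST duration tends to be too long, more so in the shorter arm, so the difference is compressed and a weak QST result would be hard to interpret. The possible loss ranges from large (a 4 SD block) to small (2 SD, or a fade), with no gain from a margin for weak long effects. These sizes rest on assumed durations, independent normal noise and an assumed wear-off shape.

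**What to change.** 1. Correct section 13.5 so that QST failure is a mean at or below the same session's treated-cheek Baseline at two consecutive time points, in line with the synopsis and Appendix 2. This is a text edit and needs no new data.

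2. Keep the zero-margin rule as the primary definition, and leave the real-time discontinuation rule as it is. Before unblinding, pre-specify one sensitivity analysis of QST duration with a margin of 1 SD of a two-reading mean.
   - Estimate that SD once from blinded pre-dose data: the SD of the same-cheek differences between screening and session Baseline means, divided by √2 (up to 76 × 2 = 152 pairs).
   - State that the 48.5°C entry limits truncate these pairs and that between-visit variation may overstate the noise. In simulated checks the estimator returned 0.83 to 1.41 times the true SD.
   - Count a mean of 51°C as a Responder. Headroom at the entry limit is 51 − 48.5 = 2.5°C.

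No needed reading is lost to discontinuation, because every zero-margin non-rise is also a non-rise under the margin. The cost is a little more analysis work and more sessions scored as no onset in that sensitivity analysis: about 11–13% for 2 SD blocks and about 30% for a fade from a 2 SD peak.
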